1.2 DRUG PROFILE

1.2.4 Nonclinical pharmacokinetics

The pharmacokinetics of BI 655130 were studied in cynomolgus monkeys. In mice, pharmacokinetics were performed with the mouse-specific anti-IL36R antibody, BI 674304 [[c03320876-01](#)].

1.2.5 Clinical experience

A FIH (first-in-human) trial [[c03361085-07](#)] has been conducted according to a single-blind, partially randomized, single rising dose and placebo-controlled (within dose groups) design. The study explored safety, tolerability, pharmacokinetics and pharmacodynamics of intravenously administered BI 655130 in healthy male subjects. Subjects were to receive single ascending IV doses of 0.001 mg/kg, 0.003 mg/kg, 0.01 mg/kg, 0.03 mg/kg, 0.1 mg/kg, 0.3 mg/kg, 1 mg/kg, 3 mg/kg, 6 mg/kg and 10 mg/kg body weight or placebo. The first 3 subjects of dose group 5 received only half of the planned dose of BI 655130 (0.05 mg/kg instead of 0.1 mg/kg) due to a calculation error. This led to an additional intermediate dose group of 0.05 mg/kg for which data is available.

Overall the study included 78 male subjects with 59 subjects treated with BI 655130 and 19 subjects treated with placebo.

Safety and Tolerability

Based on preliminary evaluation, in the FIH study 27 of 78 subjects (34.6%) reported at least 1 treatment-emergent AE (TEAE). This included 19 of 59 subjects (32.2%) following administration of BI 655130 and 8 of 19 subjects (42.1%) following administration of placebo. Results are summarized in [Table 1.2.5:1](#) below. There was no apparent relationship between the frequency of AEs and the dose. AEs categorized as related to treatment were observed in 3/19 (15.8%) subjects in the placebo group and in 7/59 (11.9%) subjects treated with BI 655130.

AEs were reported most frequently in the system organ classes (SOC) 'gastrointestinal disorders' (4/59 subjects [6.8%] on BI 655130 and 1/19 subjects [5.3%] on placebo), 'nervous system disorders' (5/59 subjects [8.5%] on BI 655130 and 2/19 subjects [10.5%] on placebo), 'infections and infestations' (4/59 subjects [6.8%] on BI 655130 and 0/19 subjects [0%] on placebo), and 'general disorders and administration site reaction' (4/59 subjects [6.8%] on BI 655130 and 1/19 subjects [5.1%] on placebo). AEs reported most frequently were headache (5/59 subjects [8.5%] on BI 655130 and 2/19 subjects [9.5%] on placebo), and nasopharyngitis (3/59 subjects [5.1%] on BI 655130 and 0/19 subjects [0%] on placebo). There were two AEs of moderate intensity, both considered non related to the study drug, (injection site hematoma, headache), all remaining AEs were of mild intensity.

Proprietary confidential information © 2016 Boehringer Ingelheim International GmbH or one or more of its affiliated companies

Table 1.2.5: 1

Frequency [N (%)] of subjects with related adverse events by treatment and preferred term

	Plac	BI 655130, Dose mg/kg body weight										
		0.001	0.003	0.01	0.03	0.1	0.3	1	3	6	10	0.05*
Number of subjects (%)	19 (100.0)	6 (100.0)	6 (100.0)	6 (100.0)	5 (100.0)	4 (100.0)	6 (100.0)	6 (100.0)	6 (100.0)	4 (100.0)	3 (100.0)	
Total with related AEs	3 (15.8)	1 (16.7)	1 (16.7)	1 (16.7)	0 (0.0)	0 (0.0)	1 (16.7)	0 (0.0)	2 (33.3)	0 (0.0)	1 (33.3)	
Conjunctiva hyperaemia	1 (5.3)	0 (0.0)	0 (0.0)	0 (0.0)	0 (0.0)	0 (0.0)	0 (0.0)	0 (0.0)	0 (0.0)	0 (0.0)	0 (0.0)	0 (0.0)
Nausea	0 (0.0)	0 (0.0)	0 (0.0)	0 (0.0)	0 (0.0)	0 (0.0)	0 (0.0)	0 (0.0)	1 (16.7)	0 (0.0)	1 (33.3)	
Vomiting	0 (0.0)	0 (0.0)	0 (0.0)	0 (0.0)	0 (0.0)	0 (0.0)	0 (0.0)	0 (0.0)	1 (16.7)	0 (0.0)	0 (0.0)	
Injection site reaction	0 (0.0)	0 (0.0)	0 (0.0)	0 (0.0)	0 (0.0)	0 (0.0)	0 (0.0)	0 (0.0)	1 (16.7)	0 (0.0)	0 (0.0)	
Headache	2 (10.5)	1 (16.7)	1 (16.7)	1 (16.7)	0 (0.0)	0 (0.0)	0 (0.0)	1 (16.7)	0 (0.0)	0 (0.0)	0 (0.0)	0 (0.0)

*Subjects were planned to receive treatment of 0.1 mg/kg but received an actual treatment of 0.05 mg/kg

There were no relevant changes compared to placebo for laboratory safety, including clinical chemistry, hematology, coagulation parameters, and urinalysis. No clinically relevant changes were observed in 12 lead ECGs, vital signs, physical exams and cardio-monitoring.

Pharmacokinetics

PK data for all dose groups are available. PK parameters and the mean concentration-time plot are shown in [Table 1.2.5:2](#) and [Figure 1.2.5:1](#) below. In dose group 3, 2 subjects had PK concentrations that were below the limit of quantitation, resulting in n= 4.

Proprietary confidential information © 2016 Boehringer Ingelheim International GmbH or one or more of its affiliated companies

Table 1.2.5: 2

Preliminary geometric mean (geometric CV%) PK parameters of BI655130 after IV Infusion

Dose Group#	#1	#2	#3	#4	#5A	#5
Dose	0.001 mg/kg N=6	0.003 mg/kg N=6	0.01 mg/kg N=4	0.03 mg/kg N=6	0.05 mg/kg N=3	0.1 mg/kg N=5
AUC _{0-tz} (h•μg/m L)	NC	NC	0.00652 (121)	2.08 (29.0)	9.57 (5.90)	25.1 (15.5)
C _{max} (μg/mL)	NC	NC	0.0228 (33.5)	0.413 (21.2)	0.998 (15.7)	1.96 (11.9)
t _{1/2} (day)	NC	NC	0.787 (150)	4.97 (17.3)	19.2 (23.0)	15.6 (24.0)
Dose Group#	#6	#7	#8	#9	#10	
Dose	0.3 mg/kg N=4	1.0 mg/kg N=6	3.0 mg/kg N=6	6.0 mg/kg N=6	10.0 mg/kg N=4	
AUC _{0-tz} (h•μg/m L)	113 (5.86)	420 (13.3)	1050 (7.26)	2610 (11.7)	4130 (12.1)	
C _{max} (μg/mL)	6.63 (3.28)	20.3 (13.6)	60.6 (7.17)	153 (12.7)	235 (2.79)	
t _{1/2} (day)	20.4 (11.9)	33.5 (55.4)	25.8 (13.3)	33.9 (18.7)	29.3 (26.3)	

2. RATIONALE, OBJECTIVES, AND BENEFIT - RISK ASSESSMENT

2.1 RATIONALE FOR PERFORMING THE TRIAL

BI 655130 is in development for the treatment of Generalized Pustular Psoriasis. The first trial to be conducted in GPP patients is an early stage development, proof-of-concept, phase I trial.

The rationale to perform this trial is based on the strong published human genetic linkage between the target disease GPP and the IL36 pathway targeted by BI 655130 [[R15-1421](#)] [[R14-5158](#)] and the high unmet clinical need in GPP. There is currently no drug specifically approved for the induction treatment of GPP flares. Patients presenting with a flare may progress to a life-threatening status without treatment and the current treatment options are not effective in reducing duration and severity of flares in GPP patients.

Recently, a FIH trial has been completed ([see section 1.2.5](#)) which explored safety, tolerability, pharmacokinetics, and pharmacodynamics of BI 655130 following IV infusions of single rising doses of 0,001 mg/kg up to 10 mg/kg body weight in a healthy male population. BI 655130 was safe and well tolerated.

The objective of the first GPP trial is to evaluate safety, tolerability, PK and pharmacogenomics as well as exploratory efficacy of a single dose of BI 655130 administered to patients with a flare of GPP.

The results from this trial will be the basis for health authority interactions to discuss and design the further developmental program with this compound in this rare and high unmet clinical need indication.

2.2 TRIAL OBJECTIVES

The primary objective of this trial is to investigate the safety and tolerability of BI 655130 following the intravenous administration of a single dose of 10 mg/kg in patients with a flare of GPP.

Secondary objectives are the assessment of the pharmacokinetics (PK) of BI 655130 after single dosing and the exploration of the efficacy in patients with a flare of GPP to establish proof-of-clinical-concept.

A description of the endpoints to be determined, and the observations along with specific information as how to collect the data for that information, is provided in [Section 5](#).

2.3 BENEFIT - RISK ASSESSMENT

Treatment with BI 655130 has the potential to provide benefit to patients with a flare of GPP by reducing the severity and duration of disease-related symptoms.

The patients are exposed to the risks related to the exposure to the trial medication and the risks of the study procedures.

Procedure-related risks

The use of an indwelling venous catheter for the purpose of blood sampling may be accompanied by mild bruising and also, in rare cases, by transient inflammation of the wall of the vein and local infection. In addition, in rare cases a nerve might be injured while inserting the venous catheter, potentially resulting in paresthesia, reduced sensibility, and/or pain for an indefinite period. The same risks apply to venipuncture for blood sampling.

The total volume of blood withdrawn during the entire study should not exceed 400 mL per patient. This is less than the volume of a normal blood donation (500 mL). No health-related risk to the patients is expected from this blood withdrawal.

Drug-related risks and safety measures

The clinical safety and tolerability profile of intravenous single doses of BI 655130 has been comparable to placebo in male subjects with intravenous single doses up to 10 mg/kg body weight. There have been no withdrawals for adverse events or abnormal laboratory values. There has been no death or other serious adverse events. The adverse events reported had no apparent dose or exposure relationship. There have been no dose or exposure related abnormalities in safety laboratory parameters and no safety or tolerability concerns that would preclude further clinical development of BI 655130.

Nonclinical studies support repeat-dose clinical trials of up to 13 weeks duration. In a 13-week intravenous toxicity study of BI 674304 in mice, no adverse effects of IL36R

Proprietary confidential information © 2016 Boehringer Ingelheim International GmbH or one or more of its affiliated companies

antagonism was seen at a dose (50 mg/kg, twice weekly) that was 5 fold higher than the dose that was protective in an experimental mouse colonic inflammation model.

We selected for the first trial in GPP patients 1368.11 a single dose of 10 mg/kg which was well tolerated in the previous single rising dose study and considered to be safe.

Based on the preceding FIH study, no specific drug-related risks are anticipated. Still, the following safety measures are/will be applied in this study in order to minimize the risk for the GPP patients:

- The IV administration allows to immediately discontinue further drug administration should any safety concern arise (please refer to [Section 4.1.4](#)).
- BI 655130 will be administered in a hospital setting and patients will be under close medical observation during their hospitalization (see [section 6.2](#)), as well as after their discharge and until the end of observation period. Safety will be closely monitored during site visits.
- Patients will be closely monitored for signs and symptoms of hypersensitivity reactions for 4 hours after the infusion at Visit 3. Hypersensitivity reactions should be treated according to medical standards.
- Extensive safety laboratory testing will be performed ([Table 5.2.3:1](#)).
- The investigator will have the possibility to treat the patient with a rescue medication of his/her choice. The decision to use a rescue medication will be based on the severity and progression of the disease (please refer to [section 4.2.1](#)).

Currently there are no data available to suggest interactions of BI 655130 [[c03320876-01](#)].

Retinoids (such as acitretin) and methotrexate will be permitted as background therapy (please refer to section 4.2.1).

Although rare, a potential for drug-induced liver injury (DILI) is under constant surveillance by sponsors and regulators. Therefore, this study requires timely detection, evaluation, and follow-up of alterations in selected liver laboratory parameters to ensure patients' safety.

Based on the findings in the nonclinical studies conducted to date and in accordance with international regulatory guidelines, the inclusion of women of childbearing potential in this study is justified [[c03320876-01](#)]. To minimize the risk of unintentional exposure of an embryo or fetus to the investigational drug, women of childbearing potential must agree to

Proprietary confidential information © 2016 Boehringer Ingelheim International GmbH or one or more of its affiliated companies

the requirements for pregnancy testing (the day before the study drug administration, and every 4 weeks thereafter until the EOT Visit) and contraceptive methods described in the patient information. Male patients will be asked to use condoms to avoid exposure of the partner via seminal fluid and prevent the partner to become pregnant if she is of childbearing potential. Birth control methods must be used for 20 weeks after the infusion (corresponding to five BI 655130 half-lives).

Considering the medical need of the development of an effective and well tolerated drug for the therapy of GPP flares, the benefit of this trial is considered to outweigh the potential minimal risks and justifies the administration of a single dose of BI 655130 10 mg/kg to patients with a flare of GPP to investigate safety, tolerability, pharmacokinetics, and efficacy.

Proprietary confidential information © 2016 Boehringer Ingelheim International GmbH or one or more of its affiliated companies

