5.6 BIOMARKER(S)

5.6.3 Methods of sample collection

Biomarkers sampling times and periods may be adapted during the trial based on information obtained during trial conduct (e.g. preliminary PK/PD data), including addition of samples and visits, as long as the total blood volume taken from each patient does not exceed 500 mL. Such changes would be implemented via non-substantial CTP Amendments.

Lesional skin biopsies (for histopathologic, immunohistopathologic and RNASeq) will be performed at baseline prior to receiving treatment (Day 1) and on Day 7 (Visit 9). Optional skin biopsies may be performed on Day 14 (Visit 10). They will be collected at the site of most inflammatory (deepest red erythema) lesion. Paired non-lesional skin biopsies will also be collected at baseline. Instructions on the skin biopsy samples preparation will be reviewed by site staff prior to the first biopsy (refer to ISF).

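### Protocol Section 2.3 caps total blood at 400 mL per patient, but Section 5.6.3 lets the sponsor add biomarker sampling up to 500 mL without referring to that cap

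*Protocol*

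**What the plan says.** Protocol Section 2.3 (Benefit - Risk Assessment), under procedure-related risks, sets a whole-study limit: "The total volume of blood withdrawn during the entire study should not exceed 400 mL per patient". It supports the limit with a comparison, "This is less than the volume of a normal blood donation (500 mL"), and draws a conclusion from it: "No health-related risk to the patients is expected from this blood withdrawal".

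Protocol Section 5.6.3 (Methods of sample collection, biomarkers) allows the biomarker sampling times to be adapted while the trial runs, "including addition of samples and visits", "as long as the total blood volume taken from each patient does not exceed 500 mL". It also fixes the route: "Such changes would be implemented via non-substantial CTP Amendments".

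Neither section refers to the other. Both are current protocol text. The mismatch is not a leftover in the description of the global amendment, and no redaction explains it.

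**The concern.** Section 2.3 is where the protocol tells ethics committees and authorities what the blood sampling costs the patient. Its argument has three steps: a limit, a comparison with a donation, and a conclusion about risk. The conclusion is drawn for the volume just named, which is 400 mL. Section 5.6.3 then describes a way of adding blood draws that is governed by a higher limit. It classes any such change in advance as non-substantial.

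At stake is a patient-protection limit in people admitted with a flare of a disease that Section 1.1 calls life-threatening. If the sponsor used the Section 5.6.3 provision to its full extent, the protocol would contain no risk statement for the volume actually drawn. Its own benefit-risk limit would also be exceeded by a change it had labelled non-substantial.

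**Working it through.** No sample-size or error-rate formula applies. The check sets the two limits side by side.

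**Inputs**

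- Limit A, Section 2.3: 400 mL per patient, entire study.
- Comparator D, Section 2.3: a donation of 500 mL, with the limit described as lying below it.
- Limit B, Section 5.6.3: 500 mL total per patient, as the condition for added samples and visits.

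**Same quantity?** Yes. Section 2.3 covers all blood drawn during the study. Section 5.6.3 covers the total taken from each patient and is not restricted to biomarker blood.

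**The plan's own comparison.** A / D = 400 / 500 = 0.80. The statement that the limit is below a donation is correct at 400 mL.

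**Size of the gap.** B − A = 500 − 400 = 100 mL. Relative to A, 100 / 400 = 25%.

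**What each section permits, by total volume V**

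| Total V | Meets 5.6.3 (V ≤ 500) | Meets 2.3 (V ≤ 400) | Below a donation (V < 500) |
|---|---|---|---|
| up to 400 mL | yes | yes | yes |
| above 400, below 500 mL | yes | no | yes |
| exactly 500 mL | yes | no | no |

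The conflict therefore covers every total above 400 mL and up to 500 mL. The donation comparison fails only at the upper end point, since 500 is not less than 500. Below that point, what is lost is agreement with the stated 400 mL limit and with the risk conclusion attached to it.

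**Can either limit be rebuilt from the schedule?** No. The available text gives no volume per sample, and the PK Flow Chart is not in it. The main Flow Chart shows when PK and safety samples are due but not how much blood each needs. It cannot be said how close the planned total comes to 400 mL.

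**The case against.** The strongest reply is that the two limits can coexist. A trial that stays at or below 400 mL satisfies both sections. One may read 400 mL as the ceiling for the planned schedule and 500 mL as an outer bound for adaptations. Section 5.6.3 nowhere claims to override Section 2.3, and its bound equals the donation volume that Section 2.3 uses as its benchmark. The first part stands: there is no conflict unless sampling is expanded. The two-tier reading is possible, but the text does not state it. Section 2.3 sets its limit for the whole study with no exception for adapted sampling. Even on that reading, the risk conclusion is not written for the higher volume, so much the same edit is needed. The softer verb in Section 2.3 (should rather than must) does not reconcile two numbers.

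A reader might infer three stronger things that the documents do not support.

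- **That sites would work to different limits depending on the section they read.** Sites draw at the Flow Chart time points and handle samples by the Lab Manual. Section 5.6.3 gives a site no authority to draw more, because the provision operates through a protocol amendment, which is the sponsor's to make.
- **That the donation rationale fails throughout the extra 100 mL.** It fails only at exactly 500 mL. The 25% measures the gap between the limits, not a failure of that comparison.
- **That patients will have more than 400 mL taken.** No planned volume is shown to exceed 400 mL.

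On oversight, Section 8.1 extends ethics and authority approval to changes introduced by amendments, and the amendment form in Section 11 reserves its no-approval category for logistical or administrative changes. Calling the Section 5.6.3 changes non-substantial points the other way. The documents leave open what review a total above 400 mL would receive, so it would go too far to say that such a change would escape review.

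**Conclusion.** The inconsistency is real and is wrong as written. Two current sections give different maxima for total blood per patient, 100 mL apart, and the risk statement rests on the lower one. A sponsor amendment that took the total above 400 mL and up to 500 mL would comply with Section 5.6.3, breach Section 2.3 and lie outside the volume for which the protocol states a risk conclusion.

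The point concerns what the text permits. It depends on a future amendment and on no assumption about the planned volume, which the available text does not allow one to calculate. It has no bearing on endpoints, analysis sets, sample size or estimates. It merits correction because it concerns patient protection and is cheap to resolve. Nothing here says which figure is right.

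**What to change.** Reconcile Protocol Sections 2.3 and 5.6.3 to a single maximum total blood volume per patient over the whole study. Word the risk statement and its donation comparison in Section 2.3 for that figure, and make the condition for added samples and visits in Section 5.6.3 refer to the same figure by cross-reference. If a separate ceiling for adaptations is intended, state it in Section 2.3 so that the risk statement covers it as the overall maximum. The choice of figure belongs to the sponsor's clinical team.

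The cost is a few sentences of protocol wording and, depending on the figure chosen, less room to add biomarker samples. The SAP needs no change.

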3. DESCRIPTION OF DESIGN AND TRIAL POPULATION

3.1 OVERALL TRIAL DESIGN AND PLAN

This single dose trial is designed as open label, exploratory, phase I, multi-centre, multi-national, single arm.

A maximum of 10 patients with a flare of GPP are planned to participate. Approximately 7 study sites in 7 countries worldwide will participate. They are all specialized referral centres experienced in the management of GPP.

Each patient will receive the active drug. Only one dose will be tested (10 mg/kg) and will be administered intravenously at Visit 3.

Patients will be hospitalized during at least 4 days following the study drug administration. Thereafter, the decision of patient's discharge will be left at the discretion of the investigator and based on the evolution of the GPP flare and the patient's health status.

Overall, 14 visits are planned. The observation period will last 20 weeks to cover the whole Residual Effect Period (refer to [section 5.2.2.2](#); Figure 3.1:1). Women of childbearing potential will perform two additional visits (phone calls) to inform the site team of the result of the urine pregnancy test at Day 56 (Visit 12pc) and Day 112 (Visit 13pc).

[figure not shown]

Figure 3.1: 1

Study design

An overview of all relevant trial activities is provided in the [Flow Chart](#). For visit schedules and details of trial procedures at selected visits, refer to [Sections 6.1](#) and [6.2](#), respectively.

3.1.1 Administrative structure of the trial

The trial is sponsored by Boehringer Ingelheim (BI).

BI has appointed a Trial Clinical Monitor, responsible for coordinating all required activities, in order to

- manage the trial in accordance with applicable regulations and internal SOPs,

Proprietary confidential information © 2016 Boehringer Ingelheim International GmbH or one or more of its affiliated companies

- direct the clinical trial team in the preparation, conduct, and reporting of the trial,
- ensure appropriate training and information of local clinical monitors (CML), Clinical Research Associates (CRAs), and participating trial sites.

The trial medication will be provided by the Clinical Trial Supplies Unit (CTSU), BI Pharma GmbH & Co. KG, Biberach, Germany. An IRT vendor will be used in this trial. Details will be provided in IRT Manual available in ISF.

The trial will be conducted in each selected centre under the supervision of the Principal Investigator. A Coordinating Investigator is responsible to coordinate investigators at different centres participating in this multicentre trial. Tasks and responsibilities are defined in a contract. Relevant documentation on the participating (principal) investigators and other important participants, including their curricula vitae, will be filed in the ISF.

A central laboratory service (except for safety laboratory tests, which will be performed at the local laboratory of each site) and vendors for photodocumentation (skin lesions) and IRT (interactive response technology) will be used in this trial. Details will be provided in the applicable manuals available in the ISF.

On-site monitoring will be performed by BI or a contract research organisation appointed by BI. Data management and statistical evaluation will be done by BI according to BI SOPs.

The organization of the trial in the participating countries will be performed by the respective local BI-organization (Operation Unit (OPU) or by a Contract Research Organization (CRO) with which the responsibilities and tasks will have been agreed and a written contract filed before initiation of the clinical trial. For each OPU participating in this study, a CML will be appointed responsible for coordinating the activities required in order to manage the trial in accordance with applicable regulations and internal SOPs in the countries covered by the respective BI OPU.

Tasks and functions assigned in order to organise, manage, and evaluate the trial are defined according to BI SOPs. A list of responsible persons and relevant local information can be found in the ISF.

